## **Part B: Intralipid vs ClinOleic**

### **Primary Objective**

To evaluate metabolic, nutritional, infectious and inflammatory parameters in patients receiving SO-based lipid emulsion compared to those of patients receiving OO -based lipid emulsion.

- Primary Outcome: length of stay
- Secondary Outcomes: mortality, nutritional parameters (anthropometry, handgrip-strength, mid-arm circumference, , pre-albumin), inflammation (high sensitivity C-reactive protein; hs-CRP), documented infections, ICU stay, antibiotic-days, liver enzymes, essential fatty acid status

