## **Statistical analysis**

**Part A:** Descriptive statistics will be performed. Results will be expressed as absolute numbers and percentages, mean  $\pm$  standard deviation (SD) or median (minimum; maximum) depending on the variable types and distributions, separately for the prospective and the retrospective dataset.

For the prospective study, multivariate logistic regression will be performed to identify risk factors associated with specific PN prescription: for example, inadequate administration of PN. In addition, data from the prospective study and the retrospective chart review will be compared by unpaired t-test, Mann-Whitney-test or chi-square test as appropriate. A p value  $<0.05$  will be considered statistically significant. **Part**

**B:** For the Intralipid and the ClinOleic analysis, all variables will be tested for normal distribution (Shapiro Wilks test). *Primary outcome* is length of stay (in days). The Intralipid and ClinOleic groups will initially be compared with unpaired t-test or Mann-Whitney test as appropriate. *Secondary outcomes*: other clinical outcomes (days in ICU, antibiotic-days, infections, mortality) will also be analyzed the same way initially. For secondary outcomes that may change over time, i.e. hs-CRP, pre-albumin and other laboratory results, BMI, arm circumference, hand grip strength, changes will be compared between groups using unpaired t-test or Mann-Whitney test as appropriate. To account for possible covariate effects (eg. age, baseline BMI, Charlson comorbidity index), regression methods such as generalized linear models will be employed. All tests will be based on two-sided alternatives and a test will be considered statistically significant using alpha=0.05. SAS Enterprise Guide 4.1 software (SAS Institute Inc., Cary, NC, USA) will be used.

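### Part B tests mortality, a yes/no outcome, and infections like length of stay (t-test or Mann-Whitney), so the group comparison has no planned risk estimate or confidence interval

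*Combined protocol and SAP*

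**What the plan says.** In the Statistical analysis section, Part B opens with a normality check: "all variables will be tested for normal distribution (Shapiro Wilks test"). For length of stay, "The Intralipid and ClinOleic groups will initially be compared with unpaired t-test or Mann-Whitney test as appropriate". The secondary clinical outcomes follow the same route: "other clinical outcomes (days in ICU, antibiotic-days, infections, mortality) will also be analyzed the same way initially". Covariates are handled afterwards: "regression methods such as generalized linear models will be employed". Age, baseline BMI and the Charlson index are given as examples, with no family, link or outcome attached. The significance rule is general: "All tests will be based on two-sided alternatives and a test will be considered statistically significant using alpha=0.05".

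Part A of the same section does provide for categorical data. The prospective and retrospective datasets "will be compared by unpaired t-test, Mann-Whitney-test or chi-square test as appropriate", and logistic regression is named for risk factors. Part B names no categorical test and no risk difference, risk ratio or odds ratio.

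The Part B objectives begin the list with mortality: "Secondary Outcomes: mortality, nutritional parameters". Documented infections appear later in that list. The documents do not say whether an infection outcome means any infection or the number per patient.

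**The concern.** Death in hospital is recorded as 0 or 1. A normality test on such data has a foregone result, and a rank test on it yields a p-value with no measure of how far the two risks differ. The section on Significance says that the results should help set standards of practice. A reader deciding between two emulsions for that purpose needs the absolute or relative difference in risk and its uncertainty, above all when the result is not significant. As the plan is written, the first-line analysis of mortality need not produce either. The same holds for infections if they are analysed as any versus none.

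**Working it through.** **Inputs.** 150 patients per group, allocated one to one (Feasibility and Sample Size); two-sided alpha 0.05 (Statistical analysis). The plan gives no event rate, effect size or power for mortality or infections, so there is no figure of its own to reproduce on this point. The event counts below are illustrations. The only infection rates that help set a scale are 1.3% to 39% for bloodstream infection (Introduction) and 40% for pneumonia, abscess or line infection in one cited study (Background). Mortality has none, so a wide range of rates was scanned.

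**Step 1: what the rule reports.** Take 15 versus 27 events.

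- Medians: 135 of 150 and 123 of 150 patients score 0, so both medians are 0.
- Rank shift (median of all 150 × 150 = 22,500 pairwise differences): (135 × 123 + 15 × 27) / 22,500 = 17,010 / 22,500 = 75.6% of the differences are exactly 0, 27 × 135 / 22,500 = 16.2% are +1 and 15 × 123 / 22,500 = 8.2% are −1. The median difference is 0.
- Risk difference: 27/150 − 15/150 = 0.18 − 0.10 = 8.0 points.
- Newcombe 95% CI, from the Wilson limits of each risk (0.1268 to 0.2492, and 0.0615 to 0.1584): lower 0.08 − √[(0.18 − 0.1268)² + (0.1584 − 0.10)²] = 0.001; upper 0.08 + √[(0.2492 − 0.18)² + (0.10 − 0.0615)²] = 0.159. That is 0.1 to 15.9 points.

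**Step 2: whether the p-value is wrong.** On 0/1 data with N = 300, the tie-corrected Mann-Whitney statistic without continuity correction satisfies z² = X² × (N − 1)/N, where X² is the uncorrected Pearson chi-square. For 15 versus 27:

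X² = 300 × (15 × 123 − 27 × 135)² / (150 × 150 × 42 × 258) = 3.987, and z² = 3.987 × 299/300 = 3.973. Both give p = 0.046.

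| Events per 150 | t-test | Mann-Whitney | Chi-square | Fisher |
|---|---|---|---|---|
| 0 vs 4 | 0.044 | 0.044 | 0.044 | 0.123 |
| 0 vs 5 | 0.024 | 0.024 | 0.024 | 0.060 |
| 1 vs 7 | 0.032 | 0.032 | 0.032 | 0.067 |
| 15 vs 27 | 0.046 | 0.046 | 0.046 | 0.066 |

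**Step 3: overall type I error.** With the same true rate p in both groups, the exact error is the sum, over all tables (a, b) with p-value below 0.05, of C(150,a) C(150,b) p^(a+b) (1 − p)^(300−a−b).

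| True rate | t-test, Mann-Whitney, chi-square | Fisher |
|---|---|---|
| 0.5% | 0.7% | 0.01% |
| 1% | 2.9% | 0.2% |
| 1.3% | 3.9% | 0.5% |
| 2% | 4.6% | 1.2% |
| 5% | 4.8% | 2.4% |
| 10% | 5.0% | 3.3% |
| 39% | 5.1% | 3.8% |

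The largest value found is 5.7% (t-test and chi-square, at a 50% rate), where events are plentiful.

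**Step 4: the t-test branch.** The mean difference of 0/1 data is the risk difference. For 15 versus 27 its interval is also 0.1 to 15.9 points. For 0 versus 5 (3.3 points) it is 0.4 to 6.2, against 0.2 to 7.6 by Newcombe, so it is too narrow when events are very few.

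**The case against.** In favour of the plan, four things can be said. First, the planned p-value is practically that of chi-square, so naming chi-square changes nothing about significance. That is correct. Second, a t-test would give the risk difference. That is also correct, but binary data fail the normality check, so the plan's rule leads away from the t-test. Third, the comparison is only an initial one, and generalized linear models include logistic regression. They could indeed supply an odds or risk ratio, but the plan leaves open the family, the link and whether these outcomes are modelled at all. Fourth, infections may be a count, for which a rank test is defensible. This stands and calls for a definition; it does not help mortality.

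The flexible wording does not close the gap either. In Part B it chooses between two tests for numerical data, whereas Part A lists "Mann-Whitney-test or chi-square test as appropriate".

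A reader might infer from the contrast with Fisher that the planned tests produce false positives when events are few. The documents do not support this. Overall error stays below 5% at low rates, and the contrast mainly reflects Fisher's conservatism. Error does exceed 5% conditional on some event totals (12.3% with 4 events, 6.0% with 5, 6.7% with 8), but not on others (3.0% with 6, 1.5% with 7, 3.6% with 9), and uncorrected chi-square behaves identically. Nor is a sparse setting established: an expected count below 5 needs fewer than 10 events among 300 patients (under 3.3%), and most of the infection range that the documents cite lies above that.

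**Conclusion.** The point holds as a defect of estimation, not of error control. Part B prescribes for mortality a procedure meant for numerical data, and the branch to which its rule leads yields no risk difference, ratio or interval. In the 15 versus 27 illustration the rank summary shows 0 where the risks differ by 8.0 points. It would go too far to say that no risk estimate could ever emerge, since the t-test or a suitably specified regression would give one; the plan simply does not commit to either.

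This rests on three assumptions: the Shapiro-Wilk result decides between the two tests, which is the natural reading; about 150 patients per group are analysed; and, for infections, the outcome is any versus none. These are secondary outcomes, so the sample size is unaffected.

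**What to change.** In Part B of the Statistical analysis section:

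- Define the infection outcome: any documented infection (yes/no), the number per patient, or both.
- For mortality and any documented infection, replace the t-test/Mann-Whitney rule with a chi-square comparison of proportions, using an exact test if an expected count is below 5.
- Report the number and percentage with the event in each group, and the risk difference with a 95% CI (for example Newcombe).
- Specify logistic regression (binomial family, logit link) with the plan's own example covariates as the adjusted analysis, where the number of events supports it. Treatment plus age, BMI and Charlson index makes four coefficients, too many for a handful of events; in that case report the unadjusted estimate only.
- Keep rank or count methods for ICU days, antibiotic-days and any infection count.

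The cost is a few sentences and slightly more analysis, with no new data. If the exact test is used with sparse events, it brings some conservatism: Fisher's error is 0.5% at a 1.3% rate, against 3.9% for the planned tests.

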### **Study design**

This is a prospective study that will evaluate the indications of parenteral nutrition in an inpatient setting. As part of their PN prescription, patients will receive either standard lipid (Intralipid) or OO-based lipid emulsion (ClinOleic), alternately depending on their time point of PN start, i.e. one person will receive Intralipid, the next one ClinOleic, etc. We will collect information from patients that have started with parenteral nutrition during their hospitalization and that are hospitalized in medical, surgical or ICU wards. We will also collect retrospective data of 100 patients to compare if the actions of the nutrition team and results change with respect to the prospective data.

Inclusion Criteria:

- Patients 18 years or older

- Patients that are expected to require PN for 5 days or more during their hospitalization
- Patients hospitalized in medical, surgical or ICU wards
- Signed informed consent either from the patient, their legally authorized representative or a direct family member

Exclusion Criteria:

- Patients without PN during their hospitalization

**Part A:** Patients will be approached when they start with PN during their hospitalization and will be followed until their last day of PN or, if occurred before PN ends, death. **Part**

**B:** For the proposed study, we will start PN as usual, according to the patients needs. We will randomly assign patients to receive either Intralipid or ClinOleic as the lipid emulsion in the PN. The amount of calories from the lipid emulsion will be equivalent.

Patients will be followed for one week after their last day on PN and, in addition, major outcomes such as mortality and length of stay will be assessed during the entire hospitalization.

Information regarding the patients nutrition will be obtained from the hospital chart and by direct communication with the PN team (dietitian, nurse, pharmacist) after signed informed consent.

We will analyze the nutritional indications and laboratory results of patients hospitalized in different units who are starting with PN alone or in combination with enteral or oral feeding twice a week. We will use a registry to enter the data.

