Measurements: :**Part A** 1) Patient demography: age, sex; 2) Type of patient: medical, surgical and/or ICU patients; 3) Type of any surgery the patient has during hospitalization; 4) Primary indications related to parenteral nutrition, comorbidities, updated CCI (31,32); 5) Nutritional assessment: weight, height, BMI, SGA, estimated energy and protein requirements; 6) comparison of energy received as a goal vs calculated energy requirements using published equations; 7) Energy, dextrose, aminoacids and lipids received by PN.

Total energy and proteins received including enteral nutrition and oral intake. Energy provided by Propofol, if received. In case of enteral nutrition, name and amount of product used; 8) Type of line used (peripheral or central); 9) Vascular access; 10) Reason for ending PN; 11) Number of times and reasons for interruption of PN; 12) Weekly PN related laboratory results; 13) Complications secondary to PN; 14) Outcome of patient

**Part B:** We will include the same measurements as in part A, but will add some additional nutritional parameters which will be done at baseline (Day 0) and after 10 days (Day 10)

with PN. Baseline or day 0 assessments to be done prior to or within 24 hours of PN initiation. Day 10 measurements to be done on day 10 of PN administration. If the PN ends before day 10, we will consider a cutoff at day 7 of PN. This means that if the PN ends before day 7, we will not repeat the measurements or blood work. If PN ends between days 7-9 we will repeat the measurements instead of doing them on day 10 for this special cases.

The parameters to measure will be: hand grip strength (kg), mid arm circumference (cm), SGA and weight as measures of nutritional status. We will also add hs-CRP, pre-albumin, and fatty acid profile in red blood cells (RBC) and plasma to the laboratory results at both time points. Clinical outcomes (documented infections, antibiotic-days or other adverse events) will be monitored for one week post-PN. In addition, mortality and length of stay will be documented for the entire hospitalization.

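### Days in ICU is tested across ward and ICU patients together, with no split by ICU status at PN start and no counting window, so a real change in ICU stay may well be missed

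*Combined protocol and SAP*

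**What the plan says.** The Part B objectives list the secondary outcomes, among them "documented infections, ICU stay, antibiotic-days, liver enzymes, essential fatty acid status". The inclusion criteria in Study design admit "Patients hospitalized in medical, surgical or ICU wards".

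In Statistical analysis, Part B, every variable is first checked for normality with Shapiro-Wilk. For length of stay, "The Intralipid and ClinOleic groups will initially be compared with unpaired t-test or Mann-Whitney test as appropriate". For the secondary outcomes, "other clinical outcomes (days in ICU, antibiotic-days, infections, mortality) will also be analyzed the same way initially". For covariates such as age, baseline BMI and the Charlson index, "regression methods such as generalized linear models will be employed". On error rates: "All tests will be based on two-sided alternatives and a test will be considered statistically significant using alpha=0.05".

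On follow-up, the Part B measurements state that "Clinical outcomes (documented infections, antibiotic-days or other adverse events) will be monitored for one week post-PN", and that mortality and length of stay are recorded for the whole hospitalization. ICU stay is named in neither window. Nothing says whether a patient never in the ICU scores 0 or is left out, or whether ICU days before PN start count.

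**The concern.** Days in ICU in a mixed ward and ICU population is two outcomes in one: whether the patient is in the ICU at all, and for how long. The plan treats it as a single continuous variable. If ward patients score 0, the distribution is a spike at zero with a right tail, normality is rejected, and Mann-Whitney is chosen. All zeros share one rank, so the rank sum mostly reflects the number of non-zero patients in each arm. Most of those were probably in the ICU before the lipid was assigned, and the lipid cannot have changed that.

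At stake is interpretation in both directions. A real shortening of ICU stay could be reported as no difference. A significant result could not be attributed to duration, to new ICU admission, or to a chance difference in how many ICU patients each arm received. The open choices (zero or excluded, counted from admission or from PN start) also mean that two analysts could follow the plan and report different results.

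**Working it through.** **The plan's own figure.** None is given for ICU days. The 150 per arm, at power 0.8 and two-sided alpha 0.05, is for length of stay. I take 150 per arm as given.

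**Inputs from the documents.** 150 per arm, 1:1 allocation, two-sided 0.05, Shapiro-Wilk then t-test or Mann-Whitney.

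**Assumptions, because the documents are silent.** A share p = 20%, 30%, 40% or 60% is in the ICU at PN start. A further 10% of the rest enter later (varied from 0 to 15%). ICU days are log-normal with median 10 days and log-SD 0.7, rounded up to whole days. Patients never in the ICU score 0. The lipid shortens ICU stay by one third and does not change entry.

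**Step 1: how much of the test concerns duration.** Mann-Whitney compares every patient in one arm with every patient in the other. A pair carries information on duration only if both patients were in the ICU. The share ever in the ICU is q = p + 0.10(1 − p), and the informative share of pairs is q². For p = 30%, q = 0.30 + 0.07 = 0.37 and q² = 0.14. About 86% of pairs say nothing about length of ICU stay.

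**Step 2: what drives the statistic.** With no lipid effect and no later entry, the between-arm difference in ICU headcount explains about 98%, 96% and 92% of the variance of the rank sum at p = 20%, 30% and 40%. Under independent assignment, the SD of that headcount difference at p = 30% is √(2 × 150 × 0.3 × 0.7) = √63 ≈ 7.9 patients.

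**Step 3: power by simulation** (3,000 trials per row, Monte Carlo error about one percentage point).

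| In ICU at PN start (p) | Ever in ICU (q) | Pairs informative on duration (q²) | Mann-Whitney, all patients | Mann-Whitney, in ICU at PN start |
|---|---|---|---|---|
| 20% | 28% | 8% | 8% | 55% |
| 30% | 37% | 14% | 12% | 76% |
| 40% | 46% | 21% | 19% | 86% |
| 60% | 64% | 41% | 52% | 96% |

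Shapiro-Wilk rejected normality in every run checked, so Mann-Whitney is the likely route. Varying later entry from 0 to 15% moves the all-patient power from 5% to 9% at p = 20%, and from 13% to 22% at p = 40%. With no later entry, an all-patient t-test lies in between, at about 22%, 35% and 49% for p = 20%, 30% and 40%.

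**Step 4: an effect on new admission instead.** If new ICU entry among patients outside the ICU at PN start is halved from 15% to 7.5%, with p = 20–40%, the all-patient Mann-Whitney has about 12–19% power. Comparing the proportion newly admitted among those patients has about 36–45%.

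**Step 5: false positives.** With no lipid effect, every test rejects in about 5% of trials.

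**Step 6: a smaller effect.** The only effect the plan cites is 17 to 15 days, for length of stay: 2/17 ≈ 12%. At that size, power among patients in the ICU at PN start is only about 10–16% for p = 20–40%, and about 5–7% in all patients.

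**The case against.** A reader might infer that this outcome has almost no power. The documents do not support that. It needs a low ICU share, which they never give, zero-scoring, which they never state, and an effect on duration alone. If patients never in the ICU were treated as not applicable, the zeros would disappear. The comparison would then rest on everyone ever in the ICU, a group formed partly after assignment. If the lipid halved all ICU entry, the pooled test would have about 69% power at a 20% share and 99% at 50%. If entry and duration both fell by a third, it would have about 43%, 67% and 85% at 20%, 30% and 40%, close to an ICU-only test at 49%, 64% and 77%. All of this stands as a limit on the claim. However, both scenarios let the lipid prevent ICU stays that had already begun at PN start. Once only later entry can change, the pooled test is weak again (step 4).

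A reader might also infer that chance imbalance in ICU patients inflates false positives. It does not: type I error stays near 5%. The difficulty is what a significant result would mean.

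The planned regression is a fair point, since the two-group test is only the initial analysis. But its example covariates do not include ICU status, and no model for excess zeros is named.

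Finally, this is one of many secondary outcomes, and the plan claims no power for it. That limits the weight of the point but does not remove it.

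**Conclusion.** The concern holds in a conditional form. As written, days in ICU is compared in a mixed population without separating patients by ICU status at PN start, and without a window or a rule for patients never in the ICU. On the literal all-patient reading, the test mainly compares ICU headcounts. With an assumed 20–40% in the ICU at PN start, power for a one-third shorter stay is about 8–20%, against about 56–87% among patients in the ICU at PN start. At 60% the gap is about 51% against 96%, so pooling costs less as the ICU share rises.

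These figures rest on the assumed ICU share, the log-normal shape, zero-scoring and a one-third effect. The direction does not depend on the exact values, but the size does. For an effect of about 12%, neither analysis is adequate. The missing window and the missing rule for patients never in the ICU are gaps in the text whatever the ICU share.

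**What to change.** In the Part B measurements and in Statistical analysis, Part B:

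- Define ICU days as days in the ICU counted from PN start over the whole hospitalization.
- Analyse by ICU status at PN start, which is fixed before the lipid acts. Compare ICU days between arms among patients in the ICU at that point. Among the rest, compare the proportion newly admitted to the ICU.
- If one overall test is wanted, use a Mann-Whitney test stratified by ICU status at PN start (van Elteren). It is a compromise. Under the step 3 assumptions its power for a one-third shorter stay is about 33%, 56% and 74% at 20%, 30% and 40%, better than pooling but below the split analysis.
- Report deaths in the ICU alongside, because death shortens ICU stay and could look like benefit.

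The cost is wording. Patient type (medical, surgical, ICU) is already recorded; the data form need only fix it as at PN start. The downsides are two secondary comparisons in place of one, and an ICU-days result that applies only to patients in the ICU at PN start.

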## **Feasibility and Sample Size**

**Part A:** Based on previous studies, there are about 200 in-patients per year receiving PN. All patients will be assessed as per standard medical guidelines for PN and it is expected that 90% will agree to participate in the project. We calculate that we will have enrolled about 50 patients for Part A, before we start with part B. We will later include 150 more patients from Part B to have a total of 200 patients. We will compare the data obtained with 100 retrospective patients to see if the actions of the nutrition team changed since we started the project.

**Part B:** When we receive the ClinOleic in the hospital, patients will receive either SO-based lipid emulsion (Intralipid= 150 patients) or OO-based lipid emulsion (ClinOleic=150 patients) on an alternate basis (one-to-one) for the duration of the PN.

The total number of patients including part A and part B is estimated to be 350 patients. It is expected to take about one and a half years to recruit this number of patients.

For the Intralipid and ClinOleic analysis, we based our sample size on a study that evaluated the use of either SO or SO + fish oil (FO) in 206 patients with gastrointestinal or colonic cancer during 7 days after surgery and found that the patients that were given the FO treatment had significantly shorter length of stay than the SO group (Mean (SD) 15(5) versus 17(8) p= 0.041). Also, they had fewer infectious complications (50). Another study compared soybean oil and soybean oil+FO in 57 elderly patients with colorectal cancer. In the treatment group, there were fewer infectious complications and incidences of systemic inflammatory response syndrome (SIRS), and shorter lengths of hospital stay were observed(51).

Based on this, we estimate that a sample size of 150 in each group with a power of 0.8 and alpha of 0.05 will be sufficient to show a similar difference in length of stay between the two groups (soybean or ClinOleic) using the online sample size calculation provided by G.W. Snedecor & W.G. Cochran  
<http://www.biomath.info/power/ttest.htm>.

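### Length of stay is to be compared unadjusted and then by covariate regression with no stated primary analysis; one pre-specified adjusted model, including patient type at PN start, should decide

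*Combined protocol and SAP*

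**What the plan says.** All references are to the combined protocol and SAP.

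- **First analysis** (Statistical analysis, Part B). Length of stay in days is the primary outcome. "The Intralipid and ClinOleic groups will initially be compared with unpaired t-test or Mann-Whitney test as appropriate". The choice between the two tests follows a Shapiro-Wilk check.
- **Second analysis** (same paragraph, after the secondary outcomes). "To account for possible covariate effects (eg. age, baseline BMI, Charlson comorbidity index), regression methods such as generalized linear models will be employed".
- **Significance** (same paragraph). "All tests will be based on two-sided alternatives and a test will be considered statistically significant using alpha=0.05".
- **Patient type** (Study design, Measurements, Part A). The list includes "Type of patient: medical, surgical and/or ICU patients", with no time point. Part B takes over the Part A measurements. The inclusion criteria admit medical, surgical and ICU patients.
- **Sample size** (Feasibility and Sample Size, Part B). It rests on a fish-oil study with length of stay "Mean (SD) 15(5) versus 17(8) p= 0.041" and concludes: "a sample size of 150 in each group with a power of 0.8 and alpha of 0.05 will be sufficient to show a similar difference". Allocation is "on an alternate basis (one-to-one) for the duration of the PN", and no stratification by ward is stated.

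The plan does not say which analysis decides the primary outcome. It fixes neither the covariate list nor the model family and link, and it assumes no covariate R2.

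**The concern.** The word "initially", attached to the primary comparison, implies a later analysis of the same outcome, and the covariate regression is the only one described. That leaves two results for length of stay, each judged at 0.05, and no order of precedence. Two things are at stake.

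1. **Error rate.** If a significant result from either analysis could support the claim, the chance of a false positive exceeds 5%. Because the covariates and the method are given only as examples, choosing among several adjusted models could add to this.
2. **Precision.** If the unadjusted test decides, the trial sets aside prognostic baseline information that it already collects. In a cohort that mixes medical, surgical and ICU patients, it is reasonable to expect patient type to predict length of stay, although the documents give no figure for this. The plan's own inputs already fall short of 80% power without adjustment.

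**Working it through.** **Inputs.** From Feasibility and Sample Size: difference 17 - 15 = 2 days; SDs 5 and 8; 150 per arm; two-sided alpha 0.05; power 0.80. R2, the share of variance in stay explained by baseline covariates, is not in the documents and is assumed over 0.05 to 0.30.

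**Step 1: the plan's own figure.** Average variance = (5² + 8²)/2 = (25 + 64)/2 = 44.5, so SD = 6.67.
n per arm = 2 × 44.5 × (1.960 + 0.842)²/2² = 174.6, so 175. The stated 150 is not reproduced.
At 150 per arm, SE = 6.67 × √(2/150) = 0.770 and 2/0.770 = 2.60. Power is 73.8% by normal approximation and 73.5% by noncentral t.

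**Step 2: type I error if either test may carry the claim.** Under the null, the unadjusted and adjusted statistics are taken as bivariate normal with correlation √(1 - R2). The error is P(|z1| > 1.96 or |z2| > 1.96).

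| R2 (assumed) | Correlation | Type I error |
|---|---|---|
| 0.10 | 0.949 | 6.5% |
| 0.20 | 0.894 | 7.1% |
| 0.30 | 0.837 | 7.6% |

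Two independent tests would give 1 - 0.95² = 9.75%. The inflation is smaller because the two tests are highly correlated. A simulation with lognormal stay gave 7.0% to 8.1% over the same R2 range. A single pre-specified test keeps 5%.

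**Step 3: power, with 44.5 as the total variance.** Residual variance = 44.5 × (1 - R2). For R2 = 0.20 this is 35.6, SD 5.97, SE 0.689, and 2/0.689 = 2.90.

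| R2 (assumed) | Residual variance | Adjusted power (noncentral t) |
|---|---|---|
| 0 | 44.5 | 73.5% |
| 0.05 | 42.3 | 75.7% |
| 0.10 | 40.1 | 77.9% |
| 0.20 | 35.6 | 82.5% |
| 0.30 | 31.2 | 87.2% |

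The R2 needed for 80% is 1 - 150/174.6 = 0.14 (normal approximation). If the SD were 8 in both arms, n = 2 × 64 × 2.802²/4 = 251.2 and the R2 needed is 1 - 150/251.2 = 0.40.

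**Step 4: power, with 44.5 as the residual variance.** The SDs come from patients operated on for gastrointestinal or colonic cancer, a narrower group than this trial's. If patient type and other covariates add to that variance, the total is 44.5/(1 - R2).

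| R2 (assumed) | Total variance | Unadjusted power (normal approx.) | Adjusted power |
|---|---|---|---|
| 0.10 | 49.4 | 69% | 74% |
| 0.20 | 55.6 | 64% | 74% |
| 0.30 | 63.6 | 58% | 74% |

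Adjustment gains precision under both assumptions. It reaches 80% only under the first, and only if R2 is about 0.14 or more.

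**Step 5: skewed stay.** In the lognormal simulation (R2 0.10 to 0.30), power was about 75% for the unadjusted Mann-Whitney test, 78% to 86% for an adjusted linear model and 81% to 89% for an adjusted model on the log scale. The outcome scale therefore matters and should be chosen in advance.

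**The case against.** The strongest reply is that the plan already has a natural order. The sentence on the primary outcome names the t-test or Mann-Whitney test, the sample size comes from a two-group t-test calculator, and the regression only follows up covariate effects. It also stands after the secondary outcomes, so its use for length of stay is inferred. This is a fair reading, and no sentence says that either result may carry the claim. The error rates above are therefore conditional. But the plan does not state this order, and under it the first-line test still forgoes the available precision. Declaring the unadjusted test primary would equally remove the double look, but it would not recover that precision.

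Three further points stand and limit the concern.

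- The covariate list is illustrative, so patient type is not excluded. It is simply not committed to.
- A reader might infer that patient type is a clean baseline factor that can go straight into the model. The documents do not support that: the field has no time point and its categories overlap. Surgery is recorded for the whole hospitalization, and ICU stay is itself a secondary outcome. Unless it is fixed at PN start, the model could adjust for events after allocation.
- A reader might also infer that adjustment restores the lost power. The documents give no R2, and Step 4 shows a plausible case in which adjusted power never exceeds about 74%.

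**Conclusion.** The concern holds in a limited form. The plan leaves the primary analysis of length of stay unnamed between an unadjusted test and an open-ended regression, and it does not commit to patient type as a covariate.

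Type I error of about 6.5% to 7.6% applies only if either result may be claimed, with a single adjusted model and R2 of 0.1 to 0.3. The gain from adjustment is real for prognostic covariates under both variance assumptions, but its size rests on an undocumented R2: about 2 to 14 percentage points for R2 0.05 to 0.30 if 44.5 is the total variance. If 44.5 is the residual variance, adjustment avoids a fall to 58% to 69% (R2 0.3 to 0.1) but leaves power near 74%.

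The failure of 150 per arm to give 80% power is a separate sample-size issue, which adjustment may offset but does not correct. The change is worth making because it settles the deciding analysis and improves precision at little cost.

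**What to change.** Name one primary analysis in the Part B text:

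- A regression of length of stay on lipid arm, adjusted for age, baseline BMI, updated Charlson index and patient type.
- Patient type as recorded at PN start, before allocation, with a fixed coding for patients in more than one category, so that later ICU stay or surgery is not adjusted for.
- Outcome scale, family and link fixed in advance to suit skewed stay, for example a linear model on the log scale, or a GLM with log link and robust standard errors. The choice should state what the arm effect then means (a ratio rather than a difference in days).
- The arm effect with its 95% CI reported as the trial's answer.
- The unadjusted t-test or Mann-Whitney comparison labelled supportive.

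If a power gain is claimed, state the assumed R2 and whether the planning SDs are total or residual. Deal with the sample size separately.

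Cost: SAP wording and a time point and coding rule for the patient-type field. The covariates are already collected, and no extra patients are needed for this change.
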